Ventral hernia repair may be associated with significant postoperative pain. Pain is typically managed with intravenous (IV) and oral medications that come with their own risks, such as nausea, constipation, sedation, respiratory depression, increased bleeding, and/or kidney or liver dysfunction. The quadratus lumborum peripheral nerve block has been shown to produce anesthesia of the anterior abdominal wall in the T7 to L1 distribution. This study aims to evaluate if the addition of the quadratus lumborum peripheral nerve block (QLB) can improve pain scores, decrease the need for IV and oral pain medications, and/or speed the patients' return to normal activity. ~~Both presence and absence of the QLB are considered standard of care, and this study aims to understand the benefits of QLB inclusion for subjects.~~

The purpose of this study is to understand pain management in patients undergoing hernia surgery. When people have ventral hernia surgery at the UWHC, the usual approach for managing postoperative pain consists of intravenous (IV) and oral pain medications. Sometimes, a quadratus lumborum (QL) nerve block, which numbs the nerves that sense pain, is also performed before surgery to help with pain management. We want to see if the addition of this nerve block results in improved pain control and recovery for patients who are undergoing laparoscopic ventral hernia repair.

Table of contents

Schedule of Activities	6
List of abbreviations and definitions	6
1. Introduction	7
1.1 Background	7
1.2 Rationale and hypothesis	8
2. Objectives	8
2.1 Primary outcome and endpoint	8
2.2 Secondary outcomes and endpoints	8
3. Study design	9
4. Study population	9
4.1 Inclusion criteria	9
4.2 Exclusion criteria	9
4.3 Protected populations	10
5. Trial interventions	10
5.1 Allocation to intervention	10
6. Subject recruitment and consent	10
6.1 Subject identification	10
6.2 Recruitment and consent	10
7. Activities and measurements	11
7.1 Data entry	12
7.2 Subject withdrawals	13
8. Data analysis and statistical considerations	13
8.1 Sample size determination	13
9. Risks and benefits of trial participation	14
9.1 Potential risks	14
9.2 Mitigation of potential risks	14
9.3 Potential benefits and risk-to-benefit ratio	15
10. Adverse events and unanticipated problems	15
10.1 Adverse event definitions	15
10.2 Severity assessment	16
10.3 Causality assessment	16
10.4 Procedures for recording and reporting adverse events	16
10.5 Other reportable events	16
11. Trial safety monitoring	17
11.1 Data Safety Monitoring Committee	17
12. Administrative requirements	18
12.1 Good clinical practice	18
12.2 Data quality assurance	18
12.3 Study monitoring	18
12.4 Ethical consideration	18
12.5 Patient confidentiality	18
12.6 Investigator compliance	18
12.7 Subject cost and payment	19
13. Funding sources	19
14. Publication Policy	19
References	20

Schedule of activities

	Screening/ Recruit/ Procedure Visit 1	PACU Visit 2	24 hours Post-op Visit 3	48 hours Post-op Visit 4 (Inpatient/ Phone)	7 days Post-op Visit 5 (Phone)
Window	Morning of Surgery	Following surgical procedure	24 hours post-op +/- 6 hours	48 hours post-op +/- 6 hours	7 days post-op +/- 6 hours
Screening and Eligibility	X				
Informed Consent	X				
Demographics	X				
Medical History	SOC				
Randomization	X				
Quadratus Lumborum Block	X				
Standard Medical Management	SOC				
Numbness Testing ¹		X			
Pain Questionnaire ²		X	X	X	X
Concomitant Medications ³	SOC	X	X	X	X
Adverse Events	SOC	SOC	X	X	X

¹Temperature sensation will be examined using a cold sensory technique

² Pain at rest, pain with activity, opioid consumption, nausea, location of most severe pain and satisfaction with regional anesthesia technique will be assessed

³Medications that are taken at home regularly and prior to arrival on the day of surgery, surgery premedication, and all medications for nausea and pain will be recorded.

List of abbreviations and definitions

AE	Adverse event
DSMC	Data Safety Monitoring Committee
PACU	Post-Anesthesia Care Unit
POD	Post-Operative Day
QLB	Quadratus Lumborum Block
SAE	Serious Adverse Event

1. Introduction

1.1 Background

Current trends in perioperative pain management stress the importance of multimodal analgesia in an effort to reduce the dependence on opioid pain medications. Adverse effects of opioids include sedation, respiratory depression, nausea, vomiting, constipation, itching, and, most importantly, the potential for tolerance and abuse. Multimodal analgesia attempts to utilize multiple techniques, including medications and nerve block procedures, to improve postoperative analgesia. Improved postoperative pain control can enable an earlier return to normal activities for patients, not only improving patient satisfaction, but also reducing postoperative morbidity and adverse effects of opioids.

Approximately 350,000 to 500,000 ventral hernia repairs are performed each year in the United States¹. Surgeries completed laparoscopically are typically performed on an outpatient basis, allowing patients to return home the same day of surgery and treat their pain independently with prescribed pain medications. Utilization of a regional anesthesia technique may allow prolonged numbing of the nerves postoperatively and decrease the reliance on oral pain medications. Transversus abdominis plane (TAP) blocks have been shown to decrease pain scores and opioid consumption following ventral hernia repair². Quadratus lumborum (QL) blocks are newer iterations of the TAP block.

There are currently three types of the QL block, all targeting the thoracolumbar fascia surrounding the quadratus lumborum muscle^{3,4}. Injection within this fascial plane may allow local anesthetic spread into the paravertebral space, possibly explaining why QL blocks have been mapped from the T7 to T12/L1 dermatomes, covering the entire abdomen. Conversely, TAP blocks have been mapped from the T10 to T12/L1 dermatomes, only covering the abdomen below the umbilicus³⁻⁶. In the first, the QL1 block, the local anesthetic is injected within the fascial plane lateral to the QL muscle. In the second, the QL2 block, the needle trajectory is more superficial, and the local anesthetic is injected along the posterior border of the QL muscle. The third iteration, the QL3, involves a deeper, transmuscular approach with injection along the anterior border of the QL muscle^{3,4}. Our study would utilize the QL2 approach as the dermatomal distribution of the QL1 and QL2 blocks appear to be more widespread than the QL3 block, and the QL2 block may be a safer approach due to the more superficial angle of the needle³.

Additionally, the QL block has been shown to have a longer duration of analgesia when directly compared to the TAP block. A study of pediatric lower abdominal surgery revealed improved pain scores and parent satisfaction with care in the QL group compared to TAP block. This improvement persisted to the 24-hour mark⁷. In a study of postoperative pain following cesarean delivery, pain scores were improved and opioid consumption decreased with the QL block compared to the TAP block. The differences were not significant at the 1- and 6-hour marks, but were significant at the 12-, 24- and 48-hour marks, highlighting the analgesic duration of the QL block⁸.

This study aims to evaluate the efficacy of the QL block using the QL2 approach on recovery profile after laparoscopic ventral hernia repair, a commonly performed surgery, as well as contribute to the understanding of the block and its distribution of anesthesia.

1.2 Rationale and hypothesis

Thousands of patients undergo ventral hernia surgery each year. Quadratus lumborum blocks are a relatively new approach for providing analgesia to the abdominal wall. The effectiveness of quadratus lumborum blocks in reducing pain, opioid consumption, and time to discharge has not been evaluated for this surgery. We propose a prospective, single-center, randomized trial to evaluate the impact of quadratus lumborum block on patient recovery profile when performed for laparoscopic ventral hernia repair compared to a standard medical management. Standard medical management typically includes perioperative multimodal analgesia utilizing acetaminophen, opioids, non-steroidal anti-inflammatory drugs, and dexamethasone. Peripheral nerve blocks, as are offered in our study, are typically offered to patients but are not routinely performed secondary to time constraints in the operating room and surgeon or patient preference. The primary outcome of the study is pain at rest on POD1. Secondary outcomes will include pain at rest on POD 0, 2 and 7, pain with activity on POD 0, 1, 2 and 7; opioid consumption on POD 0, 1, 2 and 7; nausea in PACU; time to hospital discharge and patient satisfaction.

2. Objectives

2.1 Primary outcome and endpoint

The primary outcome in this study will be pain scores as assessed by the 11-point numeric rating scale on POD 1.

2.2 Secondary outcomes and endpoints

The secondary outcomes of this study are to compare the following perioperative variables:

Preoperative Variables:

- Baseline pain

Intraoperative Variables:

- Opioid consumption
- Additional analgesics
- Anti-emetic administration

PACU Variables:

- Pain at rest
- Pain with activity
- Nausea
- Numbness distribution
- Opioid consumption
- Time in PACU (duration)
- Time to discharge home (duration)
- Location of most severe pain

POD 1, 2, and 7 Variables:

- Pain at rest

- Pain with activity
- Opioid consumption in morphine equivalents
- Nausea necessitating treatment
- Location of most severe pain
- Satisfaction with perioperative care

3. Study design

This study is a prospective, single-center, randomized trial in which 48 subjects will be enrolled at the University of Wisconsin Hospitals and Clinics (UWHC). The details of the power analysis can be found below. These subjects must meet study eligibility criteria and be scheduled to undergo an elective laparoscopic ventral hernia repair. These subjects must also agree to undergo quadratus lumborum block for postoperative analgesia. Patients will be randomized to receive QLB in addition to medical management or medical management alone. Recovery characteristics, including pain scores, nausea, opioid consumption, duration of time in PACU and to discharge, will be evaluated.

4. Study population

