6.2 Recruitment and consent

For those patients meeting criteria, they will be approached by the anesthesiologist designated to care for them on the day of surgery. That anesthesiologist will then recruit the patient for the study in the pre-operative holding area. In order to ensure the candidate's privacy and confidentiality, the discussion will take place in pre-operative holding area with the cubicle's curtain and room door closed. In a tone of voice insufficient for others to overhear the conversation and in the presence of only those immediately accompanying the patient and those who are directly involved with the patient's care, the

candidate's eligibility will again be verified against the study enrollment criteria. For candidates with confirmed study enrollment eligibility, the study purpose, procedures, risks, benefits, and alternatives will then be discussed by a study staff member. The written information about the study provided to the candidate at the time of their check-in will be reviewed and they will be instructed to take up to 90 minutes to consider participation. A study member will conduct the informed consent discussion and obtain informed consent and a study physician will be available at all times for any consent-related questions. Any questions that the candidate may have will be answered. Undue coercion will be prevented by stressing that the potential subject does not have to agree to participation and that the future care of the potential subject will not change regardless of the decision about participation. If the candidate has no further questions and would like to participate, they will be asked to sign the written informed consent document.

7. Activities and measurements

Prior to the procedure:

The subject will be met in the preoperative area by a staff anesthesiologist, who interviews and examines the subject. A full explanation of general anesthesia and quadratus lumborum block, including risks, benefits, and alternatives, will be given and informed consent for anesthetic services obtained.

Subjects will be asked to rate their pain at rest using a Numerical Rating Scale (NRS) (0-10) where 0 represents no pain and 10 represents the worst pain imaginable.

Study Randomization:

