After completion of pre-operative check in and consent is obtained by the staff anesthesiologist, the subject will be randomized to receive or not receive QLB. Randomization will be determined by opening a sequential, pre-sealed envelope with the group assignment designated within. If assigned to the intervention arm, they will then be prepped for QLB.

Quadratus Lumborum Block Procedure:

The block will be performed in the preoperative holding room as is standard practice at UW Health at the American Center. An intravenous catheter will be placed, and the subject will be pre-medicated with midazolam and/or fentanyl as needed at the discretion of the staff anesthesiologist.

Quadratus lumborum blockade will be performed after positioning the patient in the lateral decubitus position with the assistance of ultrasound guidance in the mid-abdomen posterior to the mid-axillary line. A Stimuplex needle (B. Braun Medical Inc., Melsungen, Germany) will be inserted in-plane to the ultrasound probe until the tip of the needle is appropriately positioned. Thirty milliliters of 0.25% bupivacaine will be injected under ultrasound guidance after negative aspiration. The procedure will then be repeated on the opposite side, maintaining sterility and, again, injecting 30 mL of 0.25% bupivacaine. The Bupivacaine mixture will be mixed with 2.5mcg epinephrine/ml of solution as an intravascular marker which is standard in most peripheral nerve blocks. In a situation where a patient is less than 60kg, a weight-based adjustment will be made to adjust dosing to the clinically accepted standard of 0.25mg/kg of bupivacaine. In the rare event that sonographic views are unobtainable, the patient will be excluded from the study. This outcome is unlikely to be clinically significant as qualification for laparoscopic ventral hernia repair has its own cutoff for body mass index and blocks are very rarely abandoned. However, for patient safety, we reserve the right to abandon a block.

During the Surgical Procedure:

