7.2 Subject withdrawals

At any point prior to or during the intervention period, the subject's clinical care team or a study physician may decide the subject should be withdrawn from the study. Additionally, a subject may at any point elect to withdraw themselves from the study. If a subject is withdrawn from the study for any reason the subject will then be followed according to standard of care follow-up.

Study intervention will immediately stop and subject's clinical care team and a study physician will be immediately notified if the subject suffers a severe adverse perioperative outcome.

In the event the study method is terminated, the reason for termination will be documented on a case report form.

8. Data analysis and statistical considerations

All data will be summarized using standard descriptive statistics, including mean, standard deviation, minimum, maximum, median, inter-quartile range, and confidence intervals, as appropriate. The data will be presented graphically (where possible) using scatter plots, profile plots, or histograms. Data analyses will be performed on an intent-to-treat basis based upon assignment to a treatment arm using SAS (SAS Institute Inc., Cary, NC; version 8.2 or greater) or other statistical software. The primary analysis will consist of comparing the two groups for superiority. For all tests, statistical significance will be defined as a p-value less than 0.05. Repeated measures ANOVA will be used to analyze comparisons made across multiple time points. Patients with missing longitudinal data will be handled by either using data imputation methods to replace the missing data or via alternative analyses tolerant of missing data values. Holm-Bonferroni correction will be used to control familywise error rates for comparisons across multiple time points.

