8.1 Sample size determination

The primary outcome for this study will compare resting NRS pain scores on POD1 between the QLB and medical management groups. A previous study of laparoscopic ventral hernia surgery reported an average POD1 pain score of 4.5 +/- 2.2 NRS (Fields et al, 2015). This average pain score is in keeping with our experience with patients after having laparoscopic ventral hernia surgery at UW-Madison. We feel that a reduction in pain of 2 NRS on POD1 would be meaningful for patients and their physician teams. Therefore, we will power this study to an effect size of 2 NRS. We will accept a type 1 error rate of 0.05 and 80% power. Using these metrics, the study will require a sample size of 21 patients in each group to

detect a statistical difference. To account for patients dropping out or not completing the study, we will enroll 24 patients in each group for a total of 48 patients.

9. Risks and benefits of trial participation

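### Baseline pain, rated before randomisation, is listed in Section 2.2 as a secondary outcome to compare, and Section 8 does not say whether it enters the resting-pain analysis or the Holm family

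*Combined protocol and SAP*

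**What the plan says.** Section 2.2 opens with "The secondary outcomes of this study are to compare the following perioperative variables". Its list is grouped by phase, and the only preoperative entry is baseline pain.

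Under the pre-procedure heading of Section 7, "Subjects will be asked to rate their pain at rest using a Numerical Rating Scale (NRS) (0-10"). The randomisation step follows: "After completion of pre-operative check in and consent is obtained by the staff anesthesiologist, the subject will be randomized to receive or not receive QLB".

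Section 8 sets one threshold: "For all tests, statistical significance will be defined as a p-value less than 0.05". It assigns comparisons over several times to repeated measures ANOVA and adds that "Holm-Bonferroni correction will be used to control familywise error rates for comparisons across multiple time points". It does not list the times or endpoints in that family, and it gives baseline pain no role as a covariate or as a descriptive variable.

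Section 1.2 also lists secondary outcomes. Resting pain appears there for POD 0, 2 and 7, and baseline pain does not appear.

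**The concern.** A score taken before assignment cannot respond to the assigned treatment. Calling it an outcome to compare invites a p-value that tests the randomisation and says nothing about the block.

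The label has a second consequence. Baseline pain is resting pain on the same 0-10 scale as the PACU, POD1, POD2 and POD7 scores. An analyst who follows Section 2.2 into Section 8 could either test baseline by itself at 5% or enter it as one more time point. The second choice adds a true null to the Holm family. It also averages a zero expected difference into any between-arm main effect. At stake are the clarity of the secondary results and some power for post-operative resting pain.

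**Working it through.** **Inputs from Section 8.1.** "We will accept a type 1 error rate of 0.05 and 80% power"; "we will power this study to an effect size of 2 NRS"; the cited earlier study "reported an average POD1 pain score of 4.5 +/- 2.2 NRS"; 21 evaluable per arm, 24 enrolled. Sidedness is not stated, so two-sided is assumed.

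**Plan's own figure.** A two-sample t-test with standardised effect 2/2.2 = 0.909, alpha 0.05 and 80% power needs n = 20.002 per arm, rounded up to 21. The stated figure reproduces. Power at 21 per arm is 82%.

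**Tested alone.** With intact randomisation the true baseline difference is zero, so the chance of p < 0.05 is 5% whatever the block does.

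**Pooled into Holm.** The first step uses 0.05/m. Power of the t-test for 2 points at n = 21:
- POD1 tested separately. Three secondary times: 0.05/3 = 0.0167, 67.2%. Baseline added: 0.05/4 = 0.0125, 63.0%.
- POD1 inside the family. Four times: 0.0125, 63.0%. Baseline added: 0.05/5 = 0.0100, 59.8%.

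The loss is 4.2 or 3.2 points. In a simulation of the full Holm procedure (four post-operative times against five, a 2-point effect at all four, correlation 0 or 0.5), power per comparison fell from about 73-75% to about 67%.

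**Pooled into the ANOVA.** Assumptions that the documents do not supply: SD 2.2 at every time (only POD1 is given), a common correlation r between times including baseline, and the same effect at all four post-operative times. The SD of a patient's mean over k times is 2.2 × √[(1 + (k−1)r)/k]. For 1.5 points, r = 0.5 and n = 21:
- Four post-operative times: SD = 2.2 × √0.625 = 1.739; 1.5/1.739 = 0.862; power 77.8%.
- Baseline added: mean effect = (0 + 4 × 1.5)/5 = 1.2; SD = 2.2 × √0.6 = 1.704; 1.2/1.704 = 0.704; power 60.5%.

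For 2 points the fall is from 95.3% to 84.3%.

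**Other tests on the same assumptions.**
- Arm-by-time interaction with baseline as a time level: F on 4 and 160 df. Deviations of the arm difference from its mean are −1.2 once and 0.3 four times, with sum of squares 1.80. Noncentrality = (21/2) × 1.80/[4.84 × (1−r)], which is 7.81 at r = 0.5.
- Post-operative mean adjusted for baseline: residual variance at r = 0.5 is 3.025 − 2.42²/4.84 = 1.815; SD 1.347; 1.5/1.347 = 1.113 on 39 df.

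Power for 1.5 points, n = 21:

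| r | Main effect, 4 post-op times | Main effect, baseline added | Interaction, baseline added | Post-op mean, baseline as covariate |
|---|---|---|---|---|
| 0.3 | 88% | 74% | 43% | 93% |
| 0.5 | 78% | 61% | 58% | 94% |
| 0.7 | 69% | 51% | 83% | 98% |

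**The case against.** The strongest reply is that Section 2.2 is an inventory of data by phase and not a list of tests. It includes numbness distribution, which Section 7 assesses only in patients who had the block, and it repeats POD1 resting pain, which is the primary outcome. Section 8 begins with descriptive summaries and never says that every listed variable gets a between-arm test. This stands in part. It shows that the list is loose, but the list's own lead-in still calls its entries secondary outcomes to be compared, and nothing elsewhere withdraws baseline pain from it.

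A reader might go further and infer that the tested family contains baseline, so that the post-operative comparisons lose some 17 points of power. The documents do not support that. No section puts baseline in the ANOVA or the Holm family, and the 78% to 61% fall applies only to a main effect averaged over baseline. With baseline as a time level, the treatment signal also appears in the interaction, which at r = 0.7 has 83% power and beats either main-effect test.

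A reader might also infer that a significant baseline difference could arise only by chance. That needs everyone randomised to be analysed. Section 7 excludes patients whose sonographic views cannot be obtained, which may be discovered after assignment to the block, and Section 11.1 leaves out data from early withdrawals. Selection could therefore produce a baseline difference. It would still not be an effect of the block.

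Finally, a significant baseline p-value would probably be recognised as imbalance. That limits the harm but does not justify the label.

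**Conclusion.** The point holds as a specification error with conditional consequences. Baseline pain is classed as an outcome although the block cannot affect it, the two secondary lists disagree, and the analysis section does not settle its role. The firm cost is a 5% chance of an uninformative significant result if it is tested alone, given intact randomisation. The further costs arise only if baseline is pooled: 3 to 4 points of power at the first Holm step, and dilution of a main effect averaged over baseline. The size of that dilution rests on the assumed SD, correlation and equal effects.

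The POD1 primary is unaffected if it is tested outside the time-point family. If POD1 is inside, its first-step power moves from 63.0% to 59.8%. The planned 21 evaluable and 24 enrolled per arm do not change. That baseline is rated before assignment is read from the order of steps in Section 7.

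**What to change.** Remove baseline pain from the Section 2.2 outcomes, so that the list agrees with Section 1.2 on this item, and report it by arm as a baseline characteristic without a significance test. State in Section 8 that the outcome times for resting pain, and the Holm family, are post-randomisation only, and that baseline resting pain is a covariate in that analysis. Keeping it as a covariate matters: restricting the times without adjusting gives up a possible gain (94% against 78% for 1.5 points at r = 0.5). The gain is smaller if baseline correlates less with later pain than assumed.

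The change is an edit to Section 2.2 and a sentence in Section 8, with no new data or patients. The downside is one lost baseline p-value and one degree of freedom.

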4.1 Inclusion criteria

Each patient must meet all of the following inclusion criteria to be enrolled in the study.

- 1) The subject is scheduled for elective laparoscopic ventral hernia repair;
- 2) The subject is ≥ 18 years and ≤ 80 years;
- 3) The patient agrees to receive a quadratus lumborum block
- 4) American Society of Anesthesiologists class 1-3.

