4.3 Protected populations

Prisoners

Due to the complexity of state and federal requirements governing the participation of prisoners in research, patients who are prisoners will not be considered for participation in this trial. In the unlikely event that a subject becomes a prisoner while participating in this trial, study procedures will stop and the subject will be returned to the clinical mode used prior to the intervention period or, if desired, an alternate mode requested by the clinical care team.

Pregnancy

Patients who are known to be pregnant will be excluded from participation.

5. Trial interventions

The intervention portion of this study is the randomized assignment (1:1) to receive quadratus lumborum block plus medical management or standard medical management alone. Randomization will be accomplished using an online service (www.randomizer.org) and prefilling sealed envelopes determining each subject's intervention group. Randomization will occur immediately prior to surgery. In all other aspects, the subject will receive the standard of anesthesia care appropriate for their surgery as determined by the primary anesthesia team caring for the subject. Preoperative medications will be left at the discretion of the in-room anesthesiologist for both pain and nausea regardless of the intervention.

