The patient will be contacted via phone at 24 hours, 48 hours, and 7 days to assess satisfaction with regional anesthesia, pain at rest, pain with activity, opioid consumption, nausea, pain disturbing sleep, and location of most severe pain. Duration of hospitalization will be obtained from review of medical record. Subjects with new or persistent complaints at 7 days post-surgery that could be related to the study procedures will be offered continued follow-up by telephone. Follow-up procedures would depend greatly on the clinical presentation but could include imaging, specialist consultation or surgical intervention. Subjects without complaints will be given appropriate information for contacting the research team if such complaints arise.

Concomitant Medications:

Analgesic and anti-emetic requirements for block placement, intraoperatively, and in PACU will be extracted from the patient's electronic medical record.

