7.1 Data entry

Information extracted from the subject's medical records includes date of service, subject name, date of birth, medical record number, age, gender, height, weight, data pertaining to the subject's pain, opioid consumption and ASA classification.

All study data will be collected by a study team member on a standardized case report form (CRF) and transferred to an electronic Microsoft Excel spreadsheet suitable for export in coded format to a statistical analysis program. Data entry into electronic format will take place on a private computer away from potential viewing by non-study personnel. The paper and electronic data will be kept in the primary investigator's locked office in the Department of Anesthesiology. The computer will be pass-coded and linked to a secure Anesthesia Department server to allow access only to approved study personnel. All identifiable data will be destroyed as soon as it is no longer required after study publication and/or study conclusion, and de-identified data will be retained for 7 years per UW-Madison best practices.

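### Time to discharge is compared between arms with no account of planned same-day or overnight stay, which costs precision if some patients are booked to stay

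*Combined protocol and SAP*

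**What the plan says.** - **Outcome.** Section 1.2 ends its list of secondary outcomes with "time to hospital discharge and patient satisfaction". Section 2.2 lists "Time to discharge home (duration" under the PACU variables, and Section 3 repeats time to discharge as a recovery characteristic. Section 1.2 also names time to discharge, with pain and opioid use, as an effect of the block not yet evaluated for this operation.
- **Who can enter.** Section 1.1 says "Surgeries completed laparoscopically are typically performed on an outpatient basis". The relevant entry criterion in Section 4.1 is only that "The subject is scheduled for elective laparoscopic ventral hernia repair", and nothing in Section 4.2 restricts entry by intended length of stay. The schedule of activities heads one column "48 hours Post-op Visit 4 (Inpatient/ Phone".
- **What is recorded.** Section 7 says "Duration of hospitalization will be obtained from review of medical record", which is the actual stay. The extraction list in Section 7.1 begins "date of service, subject name, date of birth, medical record number, age, gender, height, weight" and continues with pain, opioid and ASA data. Planned stay is not in it.
- **Allocation and analysis.** Section 5 describes "randomized assignment (1:1) to receive quadratus lumborum block plus medical management or standard medical management alone" and names no stratification factor. Section 8 describes a two-group comparison and repeated measures ANOVA for outcomes across time points. It names no covariate and no method for a single duration such as time to discharge.

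**The concern.** The plan admits patients who go home within hours and patients who stay a night or more, and would compare their discharge times as one sample. A stay booked before the envelope is opened cannot be caused by the block, but a day-long stay differs from a same-day stay by far more than an analgesic block is likely to change either. Unless the analysis separates the two, booked stays become noise.

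With 24 patients per arm, one or two more booked stays on one side can hide or mimic a change of about an hour. A null or chance result on an outcome that is part of the stated rationale would then be hard to interpret. Planned stay has to be captured before allocation. Actual stay is no substitute, because treatment may affect it.

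**Working it through.** **The plan's own figure.** The only sample-size calculation (Section 8.1) is for resting pain on POD1: difference 2, SD 2.2, alpha 0.05 (taken as two-sided), power 80%. A two-sample t-test needs 20.002 per group, rounded up to 21, so the plan's figure reproduces. Enrolling 24 allows for 3/24 = 12.5% loss. There is no power, SD or target effect for time to discharge, so everything below rests on assumptions.

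**Assumed inputs.** Same-day stay: mean 4 h, SD 1.5. Planned overnight stay: mean 26 h, SD 6. 24 per arm. True shortening 1 h. The overnight share p is varied.

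**Spread of the mixed outcome.**

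- Variance = (1−p)·1.5² + p·6² + p(1−p)·(26−4)². The last term is the part due to planned stay alone.
- At p = 0.10: 2.03 + 3.60 + 0.09 × 484 = 2.03 + 3.60 + 43.56 = 49.2, so SD = 7.0 h. Planned stay contributes 43.56/49.2 = 89% of the variance.
- 95% half-width for a difference in means = 2.01 × SD × √(2/24).

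| Overnight share | SD (h) | 95% half-width (h) |
|---|---|---|
| 0% | 1.5 | 0.9 |
| 10% | 7.0 | 4.1 |
| 20% | 9.3 | 5.4 |
| 30% | 10.7 | 6.2 |

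**Chance imbalance.** One extra overnight patient in an arm moves the difference in means by 22/24 = 0.92 h, and three extra move it by 2.75 h. With binomial counts of 24 per arm, the arms differ by three or more overnight patients in about 22/36/43% of trials at 10/20/30% overnight.

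**Power for a 1 h shortening** (simulated, lognormal durations):

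| Overnight share | t-test, raw means | Rank test, unstratified | Rank test, stratified by planned stay | Log time, adjusted for planned stay |
|---|---|---|---|---|
| 10% | 10% | 51% | 63% | 72% |
| 20% | 6% | 35% | 55% | 64% |
| 30% | 6% | 23% | 46% | 59% |

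For raw means, power is about 65% with no overnight patients and about 20% at 5% overnight. Repeat simulations that differ in detail move the rank-test figures by at most about 5 points and do not change the ordering. With no true effect, all four tests reject in about 4 to 6% of trials at these shares.

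**Sensitivity to stay length.** With overnight stays of 30 h (SD 12) and approximately normal durations, the t-test falls from 62% with no overnight patients to 7% at 10%. The unstratified rank test goes 59/42/28/19% at 0/10/20/30%. The pattern is the same.

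**Effects through fewer admissions.** Under those same 30 h inputs, with no change in same-day stays, a fall in admissions from 30% to 5% has about 60% power on raw means, and a fall from 50% to 10% about 81%. A fall from 30% to 15% has about 21%.

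**The case against.** The strongest reply is that the documents describe no booked overnight stays. The mixed case load is inferred from one qualifying word in Section 1.1 and a column label. The other signs point to few admissions: Section 7 puts all three follow-ups on the telephone, Section 2.2 files the outcome under PACU, and Section 4.2 excludes recurrent and multiple hernias, ASA 4-5 and chronic opioid use. This stands, and it makes the size of the loss conditional.

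A reader might take the schedule to show that overnight stays are planned. It does not. The label only permits inpatient contact at 48 hours, and under the assumed overnight distribution only about 0.3% of such patients would still be in hospital then. Patients who are still in hospital at 48 hours may be unplanned admissions, which a planned-disposition field would not capture and which treatment could affect.

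A reader might also infer that the comparison has almost no precision for any effect. The collapse occurs only for raw means, which Section 8 does not specify for this outcome; it also allows medians and inter-quartile ranges. An unstratified rank test keeps about half its power at 10% overnight, and a large fall in admissions could be detected.

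Nor can it be said that planned stay will go unrecorded. The Section 7.1 list is not exhaustive (it omits nausea and PACU duration, which Section 7 collects), and the CRF is not in the documents. The supportable statement is that the plan does not list it.

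Finally, the trial was sized for pain. Even with no admissions, power for 1 h on means is only about 62 to 65%, which is ordinary for a secondary outcome. That is a reason not to waste precision where keeping it is cheap.

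**Conclusion.** The point holds as a conditional loss of precision on one secondary outcome. Both kinds of patient may enter, time to discharge is compared between arms, and the plan neither lists planned stay nor uses it in allocation or analysis.

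If even 5 to 10% of patients have a booked overnight stay, an unadjusted comparison of means cannot resolve an effect of about an hour. An unstratified rank test gives up roughly 12 points of power at 10% overnight (51 against 63%) and 23 points at 30% (23 against 46%) relative to the stratified version.

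These sizes depend on the assumed durations, the overnight share, the 1 h effect, and planned stay predicting actual stay. With no overnight patients nothing is lost. It would be wrong to read this as bias: randomisation keeps the comparison unbiased in expectation, and the error rate under no effect is close to nominal. The primary outcome is not touched. This is a worthwhile, inexpensive improvement.

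**What to change.** Add one CRF field for planned disposition (same-day or overnight), completed before the envelope is opened. The source can be the booking or the surgical team; Section 6.1 has the operating room schedule reviewed but does not say that it shows intended stay.

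Add one sentence to Section 8: time to discharge home will be compared by a rank test stratified by planned disposition (van Elteren), or by log duration adjusted for it. Choose one in advance, and make clear that the stratum is the planned stay, not the actual one.

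The cost is one field and one sentence, with no extra patients or procedures. The downside is that the effect is reported as a rank-based estimate or a ratio, which is less familiar than a mean difference in hours. Unplanned admissions will still add spread that this does not remove.
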